3.1.2 Intervention Groups and Duration

Lerociclib is administered as a 150 mg tablet, to be taken orally twice daily (BID).

Based on current available data, lerociclib may be administered without regard to food; however, dosing under fed conditions appeared to improve gastrointestinal tolerability. For this reason, as well as for consistency across the study population, participants in this trial will be advised to take lerociclib after eating.

All participants (1L and 2L populations) will receive an AI (letrozole) or fulvestrant plus lerociclib 150 mg BID. All participants should be treated according to the best current practice guidelines and standard of care within each institution or country where the study is conducted.

All study participants will continue therapy until disease progression (as determined by Investigator per RECIST 1.1), unacceptable toxicity, withdrawal of consent, start of a new anticancer treatment, discontinuation of the participant by Investigator, or termination of the study by the Sponsor, whichever occurs first. Following disease progression, participants will only be followed for survival, and will no longer require any scheduled assessments beyond that timepoint. Survival status will be assessed every 12 weeks regardless of the participant's reason for discontinuing study treatment.

Dose adjustments of lerociclib for toxicities are to be made according to the organ system showing the greatest degree of drug-related toxicity. Toxicities will be graded using the National Cancer Institute Common Terminology Criteria for Adverse Events, version 5.0 (NCI CTCAE v5.0).

[figure not shown]
No more than two (2) lerociclib dose level reductions in total are allowed for any participant in this study. Any toxicity that requires reduction of a study participant's lerociclib dose level more than twice will result in permanent discontinuation of lerociclib dosing for the individual participant. No lerociclib dose re-escalations are allowed for any individual participant if the participant's dose reduction was due to a lerociclib-related toxicity. In cases where the relationship of the toxicity to lerociclib is unclear, the Investigator may re-challenge the participant after discussion with the Medical Monitor.

Lerociclib dose reduction will only be performed if the participant's symptom(s) is (are) related to lerociclib in the opinion of the Investigator, and not related to the participant's underlying disease.

The total study duration will be approximately 48 months. This assumes a duration of 12 months to complete participant recruitment and a median progression-free survival (PFS) duration of 24 months, plus an additional 12 months of survival follow-up for further monitoring. The full schedule of assessments is presented in [Appendix 6.1](#).

An independent Data Safety Monitoring Board (DSMB) will be set up to periodically review and evaluate the accumulated study data for assessment of participant safety and study conduct and progress, and to make recommendations to the Sponsor concerning the continuation of the study.

Figure 3 Study Schema

Statistical analyses will be performed by line of therapy without formal comparisons between populations. [REDACTED]

3.2 Endpoints

The following endpoints will be used to evaluate the efficacy and safety of the study treatment based on the study objectives:

| Objectives | Endpoints |
|---|---|
| Primary | |
| To characterize the safety and tolerability of lerociclib in combination with endocrine therapy in participants with 1L and 2L HR+/HER2- mBC. | 
 Incidence of adverse events (AEs) and serious adverse events (SAEs) |
| Secondary | |

| Objectives | Endpoints |
|---|--|
| To investigate the efficacy of lerociclib in combination with endocrine therapy in participants with 1L and 2L HR+/HER2- mBC by line of therapy. | 
 Objective response rate (ORR), defined as the proportion of participants with a best overall response of complete response (CR) or partial response (PR) according to Response Evaluation Criteria in Solid Tumors version 1.1 (RECIST v1.1) as assessed by Investigator Clinical benefit rate (CBR), defined as the proportion of participants with a best overall response of CR, PR, or stable disease (SD) according to RECIST v1.1 as assessed by Investigator Progression-free survival (PFS), defined as the time from first dose of lerociclib until the date of documented progression of disease (PD) or death, according to RECIST v1.1 as assessed by Investigator Overall survival (OS), defined as the time from the date of first dose of lerociclib to the date of death due to any cause Duration of response (DOR), defined as the time from the date of first documented response until the date of confirmed PD or death, according to RECIST v1.1 as assessed by Investigator Time to response (TTR), defined as the time from first dose of lerociclib until the first documented response (CR or PR) |
| To further characterize the safety and tolerability of lerociclib in combination with endocrine therapy in participants with 1L and 2L HR+/HER2- mBC. | 
 Change from baseline in clinical laboratory parameters (hematology, clinical chemistry, coagulation, fasting lipid panel, and urinalysis) Change from baseline in vital signs and 12-lead electrocardiogram (ECG) parameters Clinically significant findings on physical examination |
| To assess change from baseline in global health status and quality of life (QoL) in participants with 1L and 2L HR+/HER2- mBC by line of therapy. | 
 Change from baseline in the Global Health Status/QoL Scale Score of the EORTC-QLQ-C30 Change from baseline in the Global Health Status/QoL Scale Score of the EORTC-QLQ-BR23 |

| Objectives | Endpoints |
|--|---|
| | 
 Change from baseline in the Global Health Status/QoL Scale Score of the EQ-5D-5L Change from baseline in the Global Health Status/QoL Scale Score of the FACIT Item GP-5 |
| To characterize the pharmacokinetic (PK) profile of lerociclib in combination with endocrine therapy in participants with 1L and 2L HR+/HER2- mBC. | 
 Predose and postdose concentrations of lerociclib for population PK (PopPK) analysis. |
| Exploratory | |
| | |

3.2.1 Safety Variables

- AE assessments – recorded as they occur for the duration of the study
- Clinical laboratory parameters – measured at Screening, Day 1 of each cycle, Cycle 1 Day 15, and EOT/early discontinuation (ED)
- Vital sign parameters – measured at Screening, Day 1 of each cycle, Cycle 1 Day 15, and EOT/ED
- ECG parameters – measured at Screening, Day 1 of each cycle, Cycle 1 Day 15, and EOT/ED
- Physical examinations – measured at Screening, Day 1 of each cycle, and EOT/ED
- Concomitant medication assessments – recorded as they occur for the duration of the study

3.2.2 Efficacy Variables

- Tumor evaluation assessments – measured at Screening; every 8 weeks (± 7 days) during the first 12 months and every 12 weeks (± 7 days) thereafter until disease progression, death, withdrawal of consent, loss to follow-up, participant/legally acceptable representative decision; and at end of treatment (EOT) (If PR/CR is reported, confirmation of response is required; confirmatory assessment should be performed ≥ 4 weeks after response is first documented)
- Global Health Status/QoL Scale Scores (EORTC-QLQ-C30, EQ-5D-5L, and FACIT Item GP-5) – recorded at Screening; on Day 1 of each cycle (before any other study procedures) until disease progression, death, withdrawal of consent, loss to follow-up, participant/legally acceptable representative decision; and at EOT
- Global Health Status/QoL Scale Score EORTC-QLQ-BR23 – recorded at Screening; on Day 1 of every other cycle (before any other study procedures) until disease progression, death, withdrawal of consent, loss to follow-up, participant/legally acceptable representative decision; and at EOT

3.3 Pharmacokinetic Variables

- PK blood samples for concentrations of lerociclib – recorded pre and postdose at Day 1 and Day 15 of Cycle 1 and on Day 1 of Cycles 2, 3, 4, and 5.

The detailed procedures for the population PK and exposure-response analyses, including model development and evaluation, will be described in a Pharmacometric Analysis Plan.

3.4

4 STATISTICAL METHODS

4.1 Data Quality Assurance

All tables, figures, and data listings to be included in the report will be independently checked for consistency, integrity and in accordance with standard Parexel procedures.

4.2 General Presentation Considerations

Where appropriate, confidence intervals will be presented to one more decimal place than the raw data. All analyses will be performed by line of therapy.

4.2.1 Definitions

‘Baseline’ is defined as the last available pre-treatment assessment, where treatment includes the investigational medicinal product (IMP) or any non-investigational medicinal product (NIMP).

‘End of Treatment’ is defined as the value obtained at the EOT visit. If a value for a given parameter was not collected at the EOT visit the last available value collected prior to the EOT visit may be used.

‘End of Study’ (EOS) is defined as the last available post-treatment assessment.

‘Study Day’ will be calculated relative to the date of first exposure to lerociclib. For assessments prior to first exposure, Study Day = Assessment Date – Date of First Exposure. For assessments on or after first exposure date, Study Day = Assessment Date – Date of First Exposure + 1.

The timing of events may also be presented as the Cycle Number and Day (or CXDY), where X is the cycle number and Y is the number of days since the first day of lerociclib treatment in the cycle + 1.

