| PROs: EORTC-QLQ-C30 (Version 3), EQ-5D-5L, FACIT Item GP 5 | X ^b | On Day 1 of each cycle (before any other study procedures) until disease progression, death, withdrawal of consent, loss to follow-up, or participant/legally acceptable representative decision, and at EOT. | | | | | | | |
| PRO: EORTC-QLQ-BR23 | X ^b | On Day 1 of every other cycle (before any other study procedures) until disease progression, death, withdrawal of consent, loss to follow-up, or participant/legally acceptable representative decision, and at EOT. | | | | | | | |
| Collection Of Information on New Anticancer Therapies and Pregnancy Status ^k , as Applicable | | | | | | | X | X | X |
| Survival Follow-Up | | | | | | | | | X ^k |

- a. A physical examination is to be performed on Day 1 of every cycle. According to Investigator's judgment, this can be an abbreviated physical examination.
- b. To be performed between Day -7 and Day -1. For safety laboratory collections, the Screening labs do not need to be repeated at C1D1 if C1D1 and Screening are within 7 days of each other.
- c. Results of clinical laboratory tests (hematology, clinical chemistry, coagulation, fasting lipid panel, and urinalysis) must be available prior to the administration of lerociclib on Day 1 of each cycle and on Day 15 of Cycle 1. Clinical laboratory tests may be obtained up to 24 hours prior to the scheduled visit.

- d. For female study participants who are of childbearing potential (as defined in [Appendix 4](#)) only: Serum β -hCG pregnancy testing will be performed at Screening. Serum or urine β -hCG pregnancy testing will be performed at Day 1 of each cycle before the administration of lerociclib. At any timepoint during the study, pregnancy test(s) may be performed at the discretion of the Investigator.
- e. Participants will receive 12-lead ECGs (triplicate) at predose and at 2 hours and 6 hours (\pm 10 minutes) after their lerociclib dose on Day 1 and Day 15 of Cycle 1, and then on Day 1 of Cycles 2, 3, 4, and 5. Triplicate 12-lead ECGs shall be obtained within a 5-minute period and shall be performed prior to blood draws whenever applicable. The same make and model of ECG machine should be used within each participant. In addition to triplicate 12-lead ECGs, a single 12-lead ECG will be collected (prior to blood draws) at Screening and at the EOT/ED Visit. Other than at the EOT/ED Visit, ECGs will not be conducted beyond Cycle 5 unless clinically indicated.

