6.1. Study Intervention(s) Administered

All study participants will receive lerociclib (referred to herein as the IMP) every 28 days (± 2 days), and will also receive Investigator's choice of either letrozole or fulvestrant (referred to herein as NIMPs).

All premenopausal or perimenopausal female participants, and all male participants, must be receiving goserelin for at least 28 days prior to entering the study and will remain on goserelin throughout the study, in accordance with the prescribing information and according to the study site's standard practice. The schedule for administration of goserelin for each individual participant is decoupled from the rest of the study visit schedule, and will be determined by the date of the participant's most recent dose of goserelin at the time of study entry (with "goserelin C1D1" defined as the date of the participant's most recent dose + 28 days, then every 28 days subsequently).

Details of the study interventions are provided in [Table 4](#).

Table 4: Study Intervention(s) Administered

| Intervention Label | Lerociclib | Letrozole | Fulvestrant | Goserelin |
|---------------------------------|--|--|---|--|
| Intervention Name | Lerociclib | Letrozole | Fulvestrant | ZOLADEX (goserelin acetate implant) – for pre- or perimenopausal female study participants and male participants |
| Intervention Description | Tablet taken orally, 50 mg or 150 mg, BID or as indicated in Section 6.5 | Tablet taken orally, 2.5 mg, QD | 500 mg, intramuscular injection, Q2W for initial 3 doses, then Q4W thereafter | Subcutaneous implant, 3.6 mg, Q4W |
| Type | Drug | Drug | Drug | Drug |
| Dosage Formulation | Tablet | Tablet | Solution | Implant |
| Unit Dose Strength(s) | 50 mg, 150 mg | 2.5 mg | 50 mg/mL | 3.6 mg |
| Dosage Level(s) | Starting dose: 150 mg BID or as indicated in Section 6.5 | 2.5 mg QD | Initial dose: 500 mg Q2W (Week 1 Day 1, Week 3 Day 1, Week 5 Day 1) Maintenance dose: 500 mg Q4W | 3.6 mg Q4W |
| Route of Administration | Oral | Oral | Intramuscular | Subcutaneous |
| Use | Experimental | Background intervention | Background intervention | Background intervention |
| IMP or NIMP | IMP | NIMP | NIMP | NIMP |
| Manufacturer | EQRx International, Inc. | STADApHarm GmbH and G Pharma Specialities Limited (ex-US) and Accord Healthcare (US) | EVER Neuro Pharma GmbH (ex-US) and Nanjing King-Friend Biochemical Pharmaceutical Co., Ltd. (US) | AstraZeneca AB (ex-US) and TerSera Therapeutics (US) |

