7.2.2. Replacement of Study Participants

Participants who do not ever receive the IMP (lerociclib) will be replaced. Any replacement participant will receive a new participant number.

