8.3. Adverse Events, Serious Adverse Events, and Other Safety Reporting

The definitions of AEs and SAEs can be found in [Appendix 3](#). Treatment-emergent AEs are defined as AEs starting at or after the first dose of any study intervention (NIMP or IMP). Additional details will be provided in the study SAP.

All AEs will be reported by the participant (or, when appropriate, by a caregiver, surrogate, or a legally authorized representative).

All AEs (including SAEs) occurring during the study will be reported in the eCRF. This includes all events from the time following Screening, up to and including the Post-Treatment Follow-up Phase, whether or not attributed to the IMP (lerociclib) and observed by the Investigator or the participant. Any ongoing SAEs should be followed up until resolution wherever possible.

All SAEs occurring during the study must be reported via email to BOTH the Sponsor and CRO using the Severe or Serious Adverse report form with any other supporting information per the process outlined in [Appendix 3](#) and recorded in the AE section of the eCRF. Any ongoing SAEs should be followed up until resolution wherever possible.

For deaths, the working diagnosis or cause of death as stated on a death certificate, available autopsy reports, and relevant medical reports should be sent to both EQRx International, Inc. and the Parexel Pharmacovigilance Group promptly.

Definite progression of disease under study, including signs and symptoms of progression assessed by the Investigator, should not be reported as an AE or SAE.

Death unequivocally due to disease progression, as agreed by both the Investigator and the Sponsor Medical Monitor, should be documented in the eCRF but not be reported as an SAE.

The Investigator and any qualified designees are responsible for detecting, documenting, and reporting events that meet the definition of an AE or SAE and remain responsible for following up until resolution wherever possible ([Appendix 3](#)).

The methods of recording, evaluating, and assessing causality of AEs and SAEs and the procedures for completing and transmitting SAE reports are provided in [Appendix 3](#).

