4.5 Analysis Sets

The following analysis populations will be used for presentation and analysis of data:

- Safety Analysis Set is defined as all enrolled participants who have received at least 1 dose of study intervention (IMP or NIMP).
- Full Analysis Set (FAS) is defined as all enrolled participants who were exposed to lerociclib (IMP) during the study.
- Response Evaluable (RE) Analysis Set is defined as all enrolled participants who were exposed to lerociclib during the study and who had measurable disease at baseline.

All safety analyses will be assessed using the Safety Analysis Set. PFS, OS and QoL will be assessed using the FAS. Tumor response endpoints will be assessed using the RE Analysis Set. As all participants are to receive the same treatment, all analyses will be summarized based on the planned treatment dose. Any deviations from planned treatment will be documented.

The FAS and Safety Analysis Set will be derived programmatically using study drug exposure data. The RE Analysis Set will be derived programmatically as determined by investigator assessment of baseline disease status using RECIST v1.1..

A summary of the number and percentage of participants by line of therapy for each analysis set will be presented.

A by-participant listing of analysis set details will be provided, including site, participant identifier, inclusion/exclusion flag for each set, and reason for exclusion from each set..

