4.9.1.3 Treatment-emergent Adverse Events (TEAEs)

Treatment-emergent adverse events (TEAEs) will be tabulated and are defined as those adverse events that either start or worsen in severity on or after the date/time of first dose of study treatment through 30 days after end of treatment or the day before initiation of a new antineoplastic treatment, whichever occurs first. Where dates are missing or partially missing, AEs will be assumed to be treatment-emergent, unless there is clear evidence (through comparison of partial dates) to suggest that the adverse event started prior to the first dose of study treatment or after the Post-Treatment Follow-up visit. Partial dates will be imputed per rules outlined in [Appendix 6.2](#).

An overall summary table will be created to present high level TEAE and treatment-related adverse event (TRAE) information. The following will be summarized (presenting the number of participants and number of events) by line of therapy, system organ class (SOC), and preferred term (PT):

- TEAEs
- TRAEs
- Serious TEAEs
- Serious TRAEs
- For each study treatment
 - TEAEs Leading to Drug Discontinuation
 - TEAEs Leading to Drug Reduction
 - TEAEs Leading to Drug Interruption
 - TEAEs Leading to Drug Reduction or Interruption

Additionally, the following summaries presenting the number of participants and number of events will also be created:

- TEAEs by line of therapy and PT
- TEAEs in >10% of participants by line of therapy and PT
- TRAEs by line of therapy and PT
- TEAEs by line of therapy, maximum severity grade, SOC, and PT (number of participants only)

Adverse event summaries will be ordered alphabetically for SOC, and decreasing frequency of PT within SOC for the total column (including both lines of therapy).

For each participant and each adverse event, the worst severity recorded will be attributed and used in the by-severity summaries. Similarly, the worst causality (most related to Lerociclib) will be attributed and used in the by-causality summaries. If severity or causality is missing, a conservative approach for AE assessment (implementing the worst case) will be followed.

Adverse events of special interest (AESIs) TEAEs and TRAEs will also be summarized by line of therapy, maximum severity grade, SOC, and PT for the following terms:

| AESI | Definition |
|---------------------------|-----------------------|
| Febrile neutropenia | MedDRA code #10016288 |
| Pneumonitis | MedDRA code #10035742 |

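### The baseline and treatment-emergence anchors count any NIMP and do not except background goserelin, so pre-lerociclib data can be misclassified in the primary safety analysis

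*SAP*

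**What the plan says.** **Baseline.** SAP 4.2.1: baseline "is defined as the last available pre-treatment assessment, where treatment includes the investigational medicinal product (IMP) or any non-investigational medicinal product (NIMP". The same section counts Study Day from first exposure to lerociclib.

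**Treatment emergence.** Protocol 8.3: "Treatment-emergent AEs are defined as AEs starting at or after the first dose of any study intervention (NIMP or IMP". SAP 4.9.1.3 sets its own window for onset: "either start or worsen in severity on or after the date/time of first dose of study treatment through 30 days after end of treatment". This window closes early, on the day before a new antineoplastic treatment, if that comes first. The SAP does not define *study treatment*. SAP 4.7 splits prior from concomitant medication at the first dose of study medication, also undefined.

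**Safety set.** SAP 4.5: "Safety Analysis Set is defined as all enrolled participants who have received at least 1 dose of study intervention (IMP or NIMP". Protocol 9.2 has the same rule. Protocol 7.2.2 adds: "Participants who do not ever receive the IMP (lerociclib) will be replaced".

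**Goserelin.** Protocol 6.1, Table 4, lists it as a NIMP beside letrozole and fulvestrant. Pre- and perimenopausal women and all men "must be receiving goserelin for at least 28 days prior to entering the study". Their first on-study dose (goserelin C1D1) falls 28 days after the most recent dose at study entry and then repeats every 28 days, separately from the visit schedule.

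**Timing of assessments.** Under Protocol 1.3, footnote b, Screening labs, ECG and PROs are "To be performed between Day -7 and Day -1". Screening lasts up to 42 days (Protocol 4.1), and AEs are collected from consent (Protocol 8.3.1).

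**The concern.** The baseline rule and the protocol's TEAE rule are triggered by any NIMP, and one NIMP is a background drug that part of the population takes before the trial begins. For those participants, the written rules can place the first dose of treatment before the assessments meant to serve as baseline, and before AEs that occur while the participant is still being screened.

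The primary endpoint is the incidence of AEs and SAEs on lerociclib plus endocrine therapy. Screening-period events counted as treatment-emergent would raise it. Someone given goserelin but never lerociclib could stay in the denominator and lower it. Change from baseline and CTCAE grade shifts would be missing or wrongly anchored for the affected participants. Two competent programmers could follow the text and produce different TEAE counts and different baselines.

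**Working it through.** The plan gives no figure on this point. Its only sizing figure, the ORR half-width of about 16% at n = 40, reproduces: the maximum exact Clopper-Pearson half-width is 16.2%, and 1.96 × √(0.25/40) = 15.5%. It depends on n alone, so re-anchoring by itself does not change it.

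**Step 1. Is goserelin inside the rules?** Table 4 makes it a NIMP, and SAP 4.2.1 and Protocol 8.3 both say any. The SAP's *study treatment* cannot safely be read as lerociclib alone. Protocol 9.3.2.1 glosses treatment as study intervention and names goserelin among the drugs to which events are attributed. SAP 4.8 deals with goserelin under treatment compliance. No passage makes an exception.

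**Step 2. Three readings of when the first NIMP dose occurs.**

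*Reading A: pre-entry doses count.* SAP Appendix 6.1, footnote j, puts the start of goserelin at least 28 days before lerociclib, that is, at Day -28 or earlier. The earliest day of the lab, ECG and PRO window is Day -7. The gap is at least 28 − 7 = 21 days, so none of these assessments is pre-treatment. Every AE from consent to lerociclib Day 1, up to 42 days, is treatment-emergent.

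*Reading B: only on-study doses count, and entry means consent.* Assumption: the last pre-consent dose is uniform over the 28 days before consent. Goserelin C1D1 is then uniform over the 28 days after consent. With lerociclib Day 1 at S days after consent:

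- share with goserelin before lerociclib Day 1 = min(S/28, 1)
- share with goserelin before the whole Day -7 to Day -1 window = min((S − 7)/28, 1)
- mean pre-lerociclib days counted as treatment-emergent = S²/56 for S ≤ 28, and S − 14 above that

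| Screening S (days) | Before lerociclib Day 1 | Before whole Day -7 to -1 window | Mean days counted |
|---|---|---|---|
| 7 | 25% | 0% | 0.9 |
| 14 | 50% | 25% | 3.5 |
| 21 | 75% | 50% | 7.9 |
| 28 | 100% | 75% | 14 |
| 35 | 100% | 100% | 21 |
| 42 | 100% | 100% | 28 |

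These are shares of goserelin participants, not of all participants.

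*Reading C: only on-study doses count, and entry means lerociclib C1D1.* Goserelin C1D1 is then not before lerociclib C1D1, and the problem disappears.

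**Step 3. Possible inflation of an AE incidence.** Let w be the goserelin share, q the probability of a counted event during screening, and p the incidence without screening events. None is in the documents, so all are assumptions. Taking the two as independent, the added incidence is w × q × (1 − p).

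- Low: 0.10 × 0.05 × (1 − 0.40) = 0.3 percentage points
- Middle: 0.30 × 0.15 × (1 − 0.40) = 2.7 points
- High: 0.50 × 0.30 × (1 − 0.10) = 13.5 points

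This counts every screening event in goserelin participants, as in Reading A; under Reading B it would be smaller. It also shrinks as p approaches 1, so it matters less for a category that nearly everyone experiences.

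**Step 4. Denominator.** One participant with goserelin but no lerociclib, added to a line of 50, moves a 40% incidence from 20/50 to 20/51 = 39.2%.

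**The case against.** The best counter-argument is that pre-entry goserelin was never meant to count, and several passages support it.

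- Protocol 6 defines study intervention as product intended to be given according to the protocol, which fits doses taken before entry poorly.
- Inclusion criterion 9 describes Screening and Cycle 1 Day 1 as preceding the first dose of any study intervention, for the women of childbearing potential among whom many goserelin users would fall.
- The protocol names a separate on-study goserelin C1D1, and its schedule places it in Cycle 1.
- SAP 4.8 takes the first dose date from the first entry on each drug's administration form.
- Study Day and the SAP 4.10.1.3 Screening window both run from lerociclib.

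This evidence of intent stands, and it makes Reading A unlikely to be what the authors wanted. It does not cure the rule. The definitions still say any NIMP, and study entry is undefined. SAP Appendix 6.1 marks goserelin at Screening, and a 28-day cycle decoupled from lerociclib can place a dose inside a 42-day screening period. The SAP does not say whether earlier doses are entered on the administration forms.

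Other parts of the objection also stand. Vital signs have no Day -7 restriction, so under Reading B some may precede the goserelin dose. Protocol 5 does not count people who are screened but do not participate as enrolled, which would keep many goserelin-only cases out of the Safety Analysis Set, although 5.4.1 ties enrolment to signing consent. The two biases run in opposite directions, and the net effect is unknown. AE listings carry onset dates and causality for each drug, so early events remain identifiable. Including anyone dosed with a component of the combination is a legitimate choice, because the objective concerns the combination; limiting the set to lerociclib recipients would be partly a preference.

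**Conclusion.** The concern holds as a defect in stated definitions. Baseline in the SAP and TEAEs in the protocol are anchored on any NIMP, the SAP's own TEAE anchor is undefined, and goserelin is not excepted. The consequence ranges from all goserelin participants (Reading A), through a share set by screening length (Reading B: about 50% at 14 days and 100% at 28 or more, on the uniform-dose assumption), to none (Reading C). The documents do not choose between these. Up to 42 days of pre-lerociclib AEs per affected participant could enter the primary endpoint.

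A reader might infer more than the documents support:

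- *That every goserelin participant lacks a valid baseline.* This follows only if pre-entry doses count, which criterion 9 argues against.
- *That the whole goserelin run-in feeds the TEAE count.* AEs are collected only from consent.
- *That a known fraction of the 100 participants is affected.* The goserelin share is not given.
- *That the SAP's TEAE text names NIMPs.* It says only "on or after the date/time of first dose of study treatment"; the explicit wording is in Protocol 8.3.
- *That PFS would be censored at first exposure for want of a baseline scan (SAP Table 2), or the Response Evaluable set emptied.* This needs the same literal reading, and SAP 4.5 takes measurable disease from the investigator's baseline assessment.

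The correction is still warranted before database lock, because it governs the primary endpoint and costs little.

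**What to change.** 1. In SAP 4.2.1, define baseline as the last non-missing value before the first dose of lerociclib, or of letrozole or fulvestrant if either is given earlier on study. State that background goserelin does not set this anchor.
2. In SAP 4.9.1.3, start TEAEs on or after the same anchor and define *study treatment* accordingly. Use the same anchor for the prior/concomitant split in SAP 4.7.
3. List AEs between consent and the anchor separately, as pre-treatment events.
4. In SAP 4.5, state that goserelin alone does not qualify a participant for the Safety Analysis Set. Recipients of letrozole or fulvestrant can stay in, which keeps the set consistent with the anchor.
5. Align Protocol 8.3 and 9.2, and record the change in SAP 4.13, which now reports no changes to the protocol's statistical methods.

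The cost is a few lines of SAP text and derivation code, with the protocol wording aligned at the next amendment. It needs no new data and does not affect participants' treatment.
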